2. BACKGROUND, STUDY OBJECTIVES AND SPECIFIC AIMS

2.1 Background

The COVID-19 pandemic has resulted in significant loss of life with total case and death counts increasing daily. COVID-19 vaccines are effective in preventing symptomatic disease, severe disease, disease transmission, and death. Despite the efficacy and safety of COVID-19 vaccines, many people remain hesitant about vaccination with increased hesitancy among younger individuals (less than 50 years old), Black and Hispanic adults, and those living in rural areas. Recent surveys of Veterans indicate that approximately 35% are unsure whether they will receive a vaccine, highlighting the critical need for evidence-based motivational interventions to increase COVID-19 vaccine acceptance in this population who, without vaccination, remain at risk of severe adverse outcomes and death. The overall objective of this study is to implement and test a COVID-19 vaccine acceptance intervention that is responsive to the needs of Veterans and VA healthcare providers and staff. VA healthcare providers and staff are consistently identified by patients as trusted sources of vaccine information, thereby best suited to initiate vaccine acceptance discussions with patients.

2.2 Study Objectives

The COVID-19 Vaccine Acceptance Study (CoVAcS) is a hybrid type II effectiveness-implementation study with a cluster randomized clinical trial (CRCT) of 10 Veteran Healthcare Systems (VAHCS) within 2 Veteran Health Administration (VHA) regions (VISNs) aimed at improving COVID-19 vaccine uptake through use of a vaccine acceptance intervention (VAI). The objectives of this study are:

- Conduct a one-year pragmatic CRCT of the COVID-19 VAI to increase uptake of any COVID-19
 vaccine (primary outcome) and secondarily, to increase completion of the primary COVID-19
 vaccine series in 10 VAHCS compared to usual care. As an exploratory outcome, we will compare
 rates of the seasonal flu and COVID-19 boosters between intervention and control sites.
- 2) Survey Veterans with recent primary care visits from intervention and usual care VAHCS who did and did not receive COVID-19 primary vaccination to identify correlates of COVID-19 vaccine acceptance/hesitation.

2.3 Specific Aims

The specific aims are as follows:

Aim 1: Examine the effectiveness of a Vaccine Acceptance Intervention (VAI) versus usual care on Veterans' vaccination rates in a one-year cluster randomized control trial.

Aim 2: Survey Veterans to understand what factors are associated with the decision to accept or not accept COVID-19 vaccination.

3. RANDOMIZATION

Aim 1 randomization was stratified by VHA region and covariate constrained by baseline vaccination rate [Greene EJ. (2017); Moulton LH. (2004)].

4. BLINDING

All decisions about changes to the Statistical Analysis Plan will be made by a blinded statistician who will communicate with study leadership. Study evaluators and Veterans will be blinded to study arm. No other blinding was possible in this study.

5. OUTCOMES

5.1 Aim 1

5.1.1. Primary Outcome

The primary outcome is receipt of at least one dose (one of primary series or booster) of COVID-19 vaccination in Veterans who had one or more primary care visit(s) at a VA facility participating in the trial within the past year.

5.1.2 Secondary Outcome

The secondary outcome is completion of COVID-19 primary vaccination series by a previously unvaccinated Veteran with one or more primary care visit(s) at a participating VA facility within the past year.

5.1.3 Exploratory Outcomes

Flu vaccination: Receipt of seasonal flu vaccination in all Veterans with one or more primary care visit(s) at a participating VA facility within the past year.

COVID-19 First Booster: Receipt of first COVID-19 booster by those eligible for the booster within 3 months prior to the end of the study period. This includes Veterans who were eligible and had one or more primary care visit(s) at a participating VA facility within the year prior to study period, but unboosted at the start of the trial, as well as those who completed their primary series during the trial and became eligible for the booster.

5.2 Aim 2

5.2.1 Survey

Our survey contained items from the World Health Organization (WHO) Behavioral and Social Drivers Vaccination (BeSD) Model [Brewer et al., 2017]. The BeSD model included four domains: What People Think and Feel, Social Processes, Motivation, and Practical Issues.

Other survey item domains are seasonal flu vaccine acceptance, VA primary care experience, health status, and socio-demographics.

6. SAMPLE SIZE

6.1 Aim 1

6.1.1 Primary Outcome

6.1.1.1. Original Design Assumptions

Of the 16 VAHCS in VHA region 16 and 21, 10 VAHCS agreed to participate in the study, with an average of 9 to 10 clinics per VAHCS, and an average of at least 1,000 Veterans per clinic. These numbers were based on conservative projections of the number of Veterans at the time of randomization and account for missing vaccination (i.e., misclassification) status for Veterans who may have been vaccinated outside of the VA. We hypothesize that the larger proportion of Veterans will get vaccinated (both first and fully) within 12 months in the VAI arm compared to usual care. Calculations were conducted with PASS 19 (Kaysville, Utah) using sample size for mixed models for two sample proportions with a 3-level hierarchical design assuming an intra-cluster correlation (ICC) of 0.07 for individuals within a clinic and an ICC of 0.02 for clinics within a VAHCS [Elley CR, et al. (2005)]. With a type I error rate of 0.05 (two-sided) we will have at least 90% power to detect between a 9.6% and 14.6% difference in vaccination rates assuming a rate in the usual care group ranging from 5% to 20% and a total sample size of 90,000 to 100,000. **Table 1** shows details of different scenarios.

Table 1: Detectable difference for comparing 2 proportions in a hierarchical model assuming 5 VAHCS per arm with on average 9-10 clinics per VAHCS and on average 1000 individuals per clinic, 90% power, type I error of 5% (two-sided) and level 1 ICC of 0.07 and level 2 ICC of 0.02

Total Sample Size	Clinics VAMC*	Rate in Usual	Detectable
		Care	difference
90,000	9	5%	9.7%
100,000	10	5%	9.6%
90,000	9	10%	12.0%
100,000	10	10%	11.8%
90,000	9	15%	13.5%
100,000	10	15%	13.3%
90,000	9	20%	14.6%
100,000	10	20%	14.4%

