6.1.1.2 Actual Design Parameters

Of the 16 VAHCS in VHA region 16 and 21, 10 VAHCS agreed to participate in the study (5 per arm), with median number of 9 clinics per VAHCS (range: 4 to 12) with total sample size of 338,718 (Usual Care: 190,427; Intervention: 148,291) eligible Veterans at the start of the study at each VAHCS.

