6.1.2 Secondary Outcome

Power calculations for the primary outcome (any dose) apply to the secondary outcome (completion of primary series). Since there is only one secondary outcome, no multiple testing procedures will be applied, and a type I error rate of 5% (two-sided) will also be used for the secondary outcome.

6.2 Aim 2

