8. DATA COLLECTION AND DATA FREEZE

8.1 Aim 1

Data from Aim 1 will be obtained from the VA Corporate Data Warehouse (CDW) and supplemented with data from other VA administrative data (e.g., VA COVID-19 Shared Data Resource, Medicare data). Table 2 provides the study initiation for each site and the last day of 12-month follow-up for eligible participants. In the subsequent Project Modification, we added two additional follow-up timepoints of 15 and 18 months after study site initiation. The last follow-up for any participant will be 10/19/2023 – at which point the trial database will be closed/frozen and be considered ready for final analysis.

Table 2: Study initiation and follow-up completion by study site

Study Site	Initiation Date	Follow-up	
		Completion Date	
Little Rock, AR	02/14/2022	02/13/2023	
Fayetteville, AR	02/14/2022	02/13/2023	
Las Vegas, NV	03/08/2022	03/07/2023	
Reno, NV	03/08/2022	03/07/2023	
Palo Alto, CA	03/21/2022	03/20/2023	
Northern CA, CA	03/21/2022	03/20/2023	
Honolulu, HI	03/23/2022	03/22/2023	
Fresno, CA	03/23/2022	03/22/2023	
New Orleans, LA	04/20/2022	04/19/2023	
Houston, TX	04/20/2022	04/19/2023	

8.2 Aim 2

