9.1.1 General Approach

Analyses will be based on the intent to treat principle, that is any Veteran at the start of the trial who receives VHA primary care services at a participating site within one year of the study start date (Aim 1) will be considered in the denominator of the vaccination rate regardless of whether they received the intervention. Randomization was stratified by VISN and constrained based on baseline vaccination rate; therefore, all analyses will adjust for VISN and baseline vaccination rate. Since randomization was conducted at the site level, but analyses will include individual level data, we will assess the adequacy of the randomization by comparing baseline characteristics of participants between the two groups. No statistical tests will be used to assess these comparisons. Variables will be summarized using descriptive statistics. Nominal and ordinal categorical variables will be summarized using frequencies and percentages. Continuous variables will be summarized with the following descriptive statistics: N, mean, standard deviation, median, minimum, maximum, interquartile range, and range. We will also use plots (e.g., box and whisker) to explore the distribution of the data. Both the primary and secondary outcome will be tested with an alpha of 0.05 (two-sided). All other outcomes will be considered exploratory and will not be subject to corrections for multiple testing.

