9.1.4 Analysis of the Primary Outcome

To analyze the primary outcome (receipt of any COVID vaccination), we will use a multi-level model that considers the hierarchical clustering [Guo et al. (2000)] for a binary outcome and adjusts for region (VISN) and baseline vaccination rate to estimate the difference in proportion of vaccinated Veterans at 12-months between VAI and usual care. The model will also be *a priori* adjusted for the following participant level covariates: age, race/ethnicity, gender, health care utilization one year prior to the start of the trial. We will report the difference in rates between the VAI and usual care arms and 95% confidence interval.

Sensitivity Analyses

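### The claimed 90% power (SAP Table 1, Protocol Table 4) rests on normal quantiles; with 10 randomised VAHCS and a 6-df t reference it is 77-78% before any covariate gain, and SAP 9.1.4 names no small-sample test

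*SAP*

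**What the plan says.** SAP 6.1.1.1 and Protocol 5.9 (Sample Size Determination) give the same calculation. It was run in PASS 19 as a 3-level mixed model for two proportions, with 5 VAHCS per arm, 9 or 10 clinics per VAHCS and 1,000 Veterans per clinic. The ICCs are 0.07 (individuals within clinic) and 0.02 (clinics within VAHCS), and alpha is 0.05 two-sided. The conclusion is that "we will have at least 90% power to detect between a 9.6% and 14.6% difference in vaccination rates", for usual-care rates of 5% to 20%. SAP 6.1.1.2 then reports the trial as it happened: "10 VAHCS agreed to participate in the study (5 per arm), with median number of 9 clinics per VAHCS (range: 4 to 12" clinics, with 338,718 Veterans.

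SAP 6.1.2 extends the claim to the secondary outcome: "Power calculations for the primary outcome (any dose) apply to the secondary outcome (completion of primary series".

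For the analysis, SAP 9.1.4 says "we will use a multi-level model that considers the hierarchical clustering", and SAP 9.1.1 says "all analyses will adjust for VISN and baseline vaccination rate". Section 9.1.1 sets a two-sided 5% level for both outcomes, and 9.1.4 and 9.1.5 promise 95% confidence intervals. Neither these sections nor the Analytic Plan in Protocol 5.9 names a reference distribution, a degrees-of-freedom method, a small-sample correction or a permutation test.

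**The concern.** The VAHCS is the unit of randomisation and there are ten of them. Information on how much VAHCS differ therefore comes from ten units, however many Veterans each contributes. A power formula built on normal quantiles does use the five VAHCS per arm to size the standard error. What it leaves out is that this standard error must itself be estimated on very few degrees of freedom.

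Two things follow. First, the stated pair of 5% two-sided alpha and at least 90% power may not follow from the stated inputs, which matters when a null result is interpreted. Second, if the analysis also uses normal quantiles, the 5% level is not held. The plan leaves that choice open, and SAP 9 assigns the analysis to unblinded statisticians.

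**Working it through.** **Inputs** (SAP 6.1.1.1): 5 VAHCS per arm; c = 9 or 10 clinics per VAHCS; m = 1,000 per clinic; ICCs 0.07 and 0.02; alpha 0.05 two-sided; usual-care rate p of 5, 10, 15 or 20%.

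**Step 1: reproduce the plan's table.** Design effect = 1 + (m-1)(0.07) + (c-1)(m)(0.02).

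- c = 9: 1 + 69.93 + 160 = 230.93; effective n per arm = 45,000/230.93 = 194.9.
- c = 10: 1 + 69.93 + 180 = 250.93; effective n per arm = 50,000/250.93 = 199.3.

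The two-proportion formula with pooled variance under the null, z = 1.960 and 1.282, was solved for the difference at 90% power:

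| Usual-care rate | 9 clinics: computed / printed | 10 clinics: computed / printed |
|---|---|---|
| 5% | 9.74 / 9.7 | 9.61 / 9.6 |
| 10% | 11.97 / 12.0 | 11.82 / 11.8 |
| 15% | 13.47 / 13.5 | 13.31 / 13.3 |
| 20% | 14.55 / 14.6 | 14.37 / 14.4 |

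All eight agree. The normal basis is inferred from this match; the documents name only the software and the model type.

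**Step 2: where the variance lies.** In units of p(1-p), the variance of a VAHCS mean for c = 9 is 0.02 (VAHCS) + 0.05/9 (clinic) + 0.93/9,000 (individual) = 0.02566. The shares are 77.9%, 21.7% and 0.4%. For c = 10 the VAHCS share is 79.7%.

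**Step 3: degrees of freedom.** Ten VAHCS less intercept and arm leaves 8. SAP 9.1.1 and 9.1.4 add VISN and baseline vaccination rate (taken as one term), which leaves 6. The two-sided 5% critical values are 2.306 and 2.447.

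**Step 4: power at the printed differences.** Noncentrality = d / sqrt{[p(1-p) + (p+d)(1-p-d)] / effective n}. First row: 0.097 / sqrt{(0.0475 + 0.1254)/194.9} = 3.26. Across the eight rows it is 3.26 to 3.28. The noncentral t then gives:

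- 8 df: 81.3% to 81.8%
- 6 df: 77.4% to 78.0% (a pooled standard error gives 76% to 77%)

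A simulation of binary data with the plan's ICCs, analysed at VAHCS level with arm, VISN and a non-predictive baseline covariate, gave 77.9% to 78.9% power with the 6-df t. Null rejection was 4.6% to 5.0% with the 6-df t and 9.3% to 9.7% with a 1.96 cut-off.

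**Step 5: allow for covariates.** The documents give no figure for the variance explained, so the share of VAHCS-level variance removed is varied, at 6 df:

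| Share removed | 0% | 10% | 20% | 30% | 40% | 50% |
|---|---|---|---|---|---|---|
| Power | 77-78% | 81% | 84% | 87% | 90-91% | 93-94% |

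90% power at 6 df needs noncentrality 3.91. Break-even is at 38-39% removed (37.7% to 39.4% across the rows).

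**Step 6: detectable differences at 90% power, 6 df, no covariate gain.**

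| Usual-care rate | 5% | 10% | 15% | 20% |
|---|---|---|---|---|
| 9 clinics | 12.2 | 14.7 | 16.4 | 17.6 |
| 10 clinics | 12.0 | 14.5 | 16.2 | 17.4 |

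**Step 7: type I error if 1.96 were used.** P(|t| > 1.96) = 8.6% on 8 df and 9.8% on 6 df.

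**Step 8: does the larger cohort help?** Assume 9 equal clinics per VAHCS (SAP 6.1.1.2 gives a range of 4 to 12). Then m = 190,427/45 = 4,232 in usual care and 148,291/45 = 3,295 in the intervention arm. The design effects are 974.2 and 758.9, and effective n is 195.5 and 195.4 against 194.9 planned. Power on 6 df stays at 77-78%.

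**The case against.** The strongest reply is that the table contains no arithmetic slip. It follows from its inputs under a common planning approximation, and the 77-78% figure is the low end of a range. That figure charges two degrees of freedom for VISN and baseline rate and credits them with nothing, although they were chosen because they should predict uptake. Protocol 2.0 reports 46% against 58% vaccinated by VISN, and 39% to 63% within VISN 16. This is fair as far as it goes, and is why the full range is shown. But those are cumulative rates, not 12-month uptake, so they fix no value. The plan claims no covariate gain, and even 8 df with no covariate terms falls short of 90%.

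The type I error consequence is conditional: no section commits to 1.96. That stands. The gap is that nothing rules it out.

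The 6 df comes from the SAP model. The Analytic Plan in Protocol 5.9 describes adjustment for the constrained-randomisation variables, with rurality and facility size as examples. The SAP is the more specific document for the analysis, and Protocol Table 4 is the same table, so one basis should serve both.

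Finally, the trial has been run, and a restated table changes no sample size. True; its value lies in interpretation. The reference distribution is the part that affects inference.

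**Conclusion.** The concern holds. On the stated inputs, 90% power at a two-sided 5% level is not delivered: it is 81-82% on 8 df and 77-78% on the 6 df implied by the SAP model. Equivalently, the 90%-power detectable differences are 12.0 to 17.6 points instead of 9.6 to 14.6. The claim can be rescued only if covariates remove about 38-39% of the VAHCS-level variance, which the plan does not assert. The actual cohort of 338,718 does not change this, because the limit is the number of VAHCS. The same statement and alpha carry over to the secondary outcome.

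These figures assume the plan's ICCs, equal cluster sizes, the unpooled standard error, baseline rate as a single term and, for the headline figure, no covariate gain. Unequal clinic numbers and arm sizes would tend to lower power slightly. The type I error of 8.6-9.8% applies only if normal quantiles are used in the analysis.

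**What to change.** 1. In SAP 9.1.4, applying also to 9.1.5, state that for the primary and secondary outcomes the arm effect and its 95% CI use a t reference with between-VAHCS degrees of freedom: 10 VAHCS minus 4 VAHCS-level parameters = 6. A VAHCS-level analysis of covariate-adjusted residuals on the same 6 df would be equivalent.

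   A permutation test is an option only if the constrained allocation set is large enough. SAP 3 says "Aim 1 randomization was stratified by VHA region and covariate constrained by baseline vaccination rate" but does not give the size of the set. SAP Table 2 ("Study initiation and follow-up completion by study site") lists 4 sites in VISN 16 states and 6 in VISN 21 states. With even splits within VISN (an assumption), there are 6 x 20 = 120 allocations, and the smallest two-sided p is 2/120 = 0.017. At least 40 must remain after constraint for p of 0.05 or less to be reachable (2/40 = 0.05).

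2. Restate SAP Table 1 and Protocol Table 4 on the same 6 df, either as 77-78% power at the listed differences or with the detectable differences in Step 6. Say that no covariate variance reduction is assumed, or give the reduction and its source. The original figures can be kept alongside as the planning record.

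The cost is one sentence and two tables, with no new data. The downside is a less favourable stated power and a 95% CI about 25% wider than with normal quantiles (2.447/1.960 = 1.25). SAP 9 allows changes until data lock and before unblinding. SAP 8.1 closes the database at last follow-up on 10/19/2023, and the documents do not show whether the window is still open. If it has closed, the addition should be dated and declared as made after lock.

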6.1.1.2 Actual Design Parameters

Of the 16 VAHCS in VHA region 16 and 21, 10 VAHCS agreed to participate in the study (5 per arm), with median number of 9 clinics per VAHCS (range: 4 to 12) with total sample size of 338,718 (Usual Care: 190,427; Intervention: 148,291) eligible Veterans at the start of the study at each VAHCS.

6.1.2 Secondary Outcome

Power calculations for the primary outcome (any dose) apply to the secondary outcome (completion of primary series). Since there is only one secondary outcome, no multiple testing procedures will be applied, and a type I error rate of 5% (two-sided) will also be used for the secondary outcome.

6.2 Aim 2

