Sample Size Determination: Of the 16 VAHCS in VHA region 16 and 21, 10 VAHCS agreed to participate in the study, with an average of 9 to 10 clinics per VAHCS, and an average of at least 1,000 Veterans per clinic. These numbers were based on conservative projections of the number of Veterans at the time of randomization and account for missing vaccination (i.e., misclassification) status for Veterans who may have been vaccinated outside of the VA. We hypothesize that the larger proportion of Veterans will get vaccinated (both first and fully) within 12 months in the VAI arm compared to usual care. Calculations were conducted with PASS 19 (Kaysville, Utah) using sample size for mixed models for two sample proportions with a 3-level hierarchical design assuming an intra-cluster correlation (ICC) of 0.07 for individuals within a clinic and an ICC of 0.02 for clinics within a VAHCS.¹¹⁴ With a type I error rate of 0.05 (two-sided) we will have at least 90% power to detect between a 9.6% and 14.6% difference in vaccination rates assuming a rate in the usual care group ranging from 5% to 20% and a total sample size of 90,000 to 100,000. **Table 4** shows details of different scenarios.

Table 4: Detectable difference for comparing 2 proportions in a hierarchical model assuming 5 VAHCS per arm with on average 9-10 clinics per VAHCS and, on average, 1000 individuals per CBOC/clinic, 90% power, type I error of 5% (two-sided) and level ICC of 0.07 and level 2 ICC of 0.02

| Total Sample Size | Clinics VAMC* | Rate in Usual Care | Detectable difference |
|-------------------|---------------|-----------------------|--------------------------|
| 90,000 | 9 | 5% | 9.7% |

| 100,000 | 10 | 5% | 9.6% |
|---------|----|-----|-------|
| 90,000 | 9 | 10% | 12.0% |
| 100,000 | 10 | 10% | 11.8% |
| 90,000 | 9 | 15% | 13.5% |
| 100,000 | 10 | 15% | 13.3% |
| 90,000 | 9 | 20% | 14.6% |
| 100,000 | 10 | 20% | 14.4% |

*Only presented 9 and 10 clinics per VAMC for baseline rate of 5%- a negligible difference in the detectable difference between 9 and 10.

These calculations are for both the primary outcome (any dose) and secondary outcome (primary vaccination series completion). Since there is only one secondary outcome, no multiple testing procedures will be applied, and a type I error rate of 5% will also be used for this outcome.

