	treatment groups using a multi-level model that accounts for the		
	hierarchical clustering and adjusts for baseline vaccination rate at the VAHCS		
	facility, region (VISN), age, race/ethnicity, gender, and health care utilization		
	one year prior to the start of the trial. The difference will be tested at the		
	0.05 level of significance (two-sided).		
Heterogeneity of	We will describe the variation in treatment response on the primary		
Treatment Effect			
(HTE) Analyses	groups.		
. , ,			

Secondary Outcomes	Aim 1: Completion of the COVID-19 primary vaccine series.
Exploratory Outcomes	Aim 1: Receipt of COVID-19 booster; receipt of seasonal flu vaccination.
Interim Analysis	No interim analyses were proposed.

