9.1.5 Analysis of Secondary Outcome

We will use the same hierarchical, multi-level method for binary outcomes to analyze the secondary outcome of primary series completion in Veterans reported to not have initiated or completed the COVID-19 primary series at randomization. The model structure and adjustments are identical to that

for the primary outcome in Section 9.1.4. No multiple testing will be considered since there is only one secondary outcome. We will report the difference in rates between the VAI and usual care arms and the 95% confidence interval.

Sensitivity Analyses

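### The primary and secondary outcomes are each tested at two-sided 5% with no order between them, and the reason given does not cover that pair of tests

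*SAP*

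**What the plan says.** SAP 9.1.1 gives a significance level to exactly two outcomes: "Both the primary and secondary outcome will be tested with an alpha of 0.05 (two-sided"). It sets the rest aside: "All other outcomes will be considered exploratory and will not be subject to corrections for multiple testing".

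The reason for having no multiplicity procedure is the same wherever one is given. SAP 6.1.2 has "Since there is only one secondary outcome, no multiple testing procedures will be applied, and a type I error rate of 5% (two-sided"), SAP 9.1.5 has "No multiple testing will be considered since there is only one secondary outcome", and protocol 5.9 (Aim 1 sample size) has "Since there is only one secondary outcome, no multiple testing procedures will be applied". Protocol 5.9 repeats it under the analysis of the secondary outcome.

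The two outcomes differ in event and population:

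- Primary (SAP 5.1.1): "The primary outcome is receipt of at least one dose (one of primary series or booster) of COVID-19 vaccination in Veterans" with a recent primary care visit, whatever their earlier vaccination status.
- Secondary (SAP 5.1.2): "The secondary outcome is completion of COVID-19 primary vaccination series by a previously unvaccinated Veteran".

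Neither document contains a testing order, a gate, a split of alpha, or a rule for reading the secondary result after a null primary. Interim looks add nothing to the error rate: "No interim analyses were proposed".

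**The concern.** The stated reason counts only secondary outcomes, but a joint error rate depends on the number of tests that can support a claim. Here that number is two.

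The plan does not treat the secondary outcome as purely descriptive. Protocol 3.0 and 5.9 state it as a directional hypothesis (H1b) beside the primary (H1a), and label only the later ones exploratory. SAP 6.1.2 carries the primary's power calculation over to it. The sample size text in both documents expects benefit on first doses and on full vaccination.

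The awkward case is a null result for any dose with series completion at p < 0.05. The two outcomes carry different messages: one covers all eligible Veterans and counts boosters, the other covers only those not previously vaccinated. The plan does not say whether the second result would then be a confirmatory finding or a supportive one, so that decision could be made after the results are known.

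**Working it through.** **Inputs from the documents.** Two tests, each at two-sided 0.05 (SAP 6.1.2, 9.1.1). No interim analysis (SAP 1). Stated power 90% for the primary, carried over to the secondary (SAP 6.1.1.1, 6.1.2). Design: 5 systems per arm, K = 9 or 10 clinics per system, M = 1,000 Veterans per clinic, ICCs 0.07 and 0.02.

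**Assumptions.** The test statistics are bivariate normal, each test holds its nominal 5%, and their correlation ρ is not negative. The documents do not give ρ, so a range is shown.

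**Step 1: the plan's own figure.** Design effect f = 1 + (M − 1) × 0.07 + M(K − 1) × 0.02; effective size per arm = 5KM/f.

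- K = 9: f = 1 + 69.93 + 160 = 230.93; 45,000/230.93 = 194.9.
- K = 10: f = 1 + 69.93 + 180 = 250.93; 50,000/250.93 = 199.3.

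A pooled two-proportion test at two-sided 0.05 then has power 0.898 to 0.902 in all eight rows of SAP Table 1. The stated 90% is reproduced and is used in step 4. The documents give no familywise rate to reproduce.

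**Step 2: joint error with both nulls true.** The chance of at least one rejection is 1 − P(|Z1| < 1.96 and |Z2| < 1.96). At ρ = 0 this is 1 − 0.95² = 9.75%. The bound that needs no distributional assumption is 0.05 + 0.05 = 10%.

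**Step 3: false claims of benefit only.** The chance is 1 − P(Z1 < 1.96 and Z2 < 1.96). At ρ = 0 this is 1 − 0.975² = 4.94%. One two-sided 5% test gives 2.5%.

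**Step 4: chance of a secondary claim under a fixed sequence.** This is P(Z1 > 1.96 and Z2 > 1.96), with each test at 90% power on its own. At ρ = 0 it is 0.9 × 0.9 = 81%.

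| ρ (assumed) | Any false rejection | False claim of benefit | Secondary claim, fixed sequence |
|---|---|---|---|
| 0 | 9.75% | 4.94% | 81.0% |
| 0.3 | 9.51% | 4.76% | 82.2% |
| 0.5 | 9.07% | 4.54% | 83.2% |
| 0.7 | 8.35% | 4.17% | 84.7% |
| 0.9 | 7.04% | 3.52% | 86.9% |
| 0.99 | 5.66% | 2.83% | not computed |

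The any-rejection figure falls below 8% once ρ exceeds about 0.77. If the primary had only 50% power and the secondary 90%, the chance of a secondary claim under the sequence would be 45% (ρ = 0) to 50% (ρ = 0.9).

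**Step 5: error under the fixed sequence.** If the primary null is true, any false rejection requires the primary to be rejected first, which has probability 5%. If only the secondary null is true, its own test limits the error to 5%. The familywise rate is therefore at most 5% for any ρ.

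**The case against.** The strongest reply is that no stated error rate is breached. The documents set 5% per test and never claim control across the two outcomes. One outcome is plainly named primary, its test keeps 5% whatever happens to the other, and the choice is disclosed. Whether one clearly labelled secondary outcome in a pragmatic trial needs formal gatekeeping is partly convention. All of that stands. It limits how serious the point is, but it does not repair the reason given.

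A reader might infer three stronger things that the documents do not support:

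- **That the joint error is 8-10%.** This needs a correlation below about 0.77, which is nowhere stated. Completing the series during the trial generally also counts as a primary event, and both outcomes use the same ten sites and the same model, so the correlation could be high. Boosters in already vaccinated Veterans pull the other way. The value is unknown.
- **That the plan licenses an effectiveness claim on the secondary alone.** No section says so. The plan is silent, and the gap is that it does not rule the claim out.
- **That a fixed sequence costs nothing.** It costs the primary nothing, but it removes the secondary claim after a null primary.

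**Conclusion.** The point holds as a gap in the testing rule and a faulty reason for it. It is a cheap improvement and does not threaten the primary analysis.

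With both nulls true, the chance of at least one rejection lies above 5% and reaches at most about 9.75% under the normal approximation. The position in that range depends on the undocumented correlation. The figure counts rejections in either direction. For false claims of benefit the ceiling is 4.9% against 2.5% for one test, so the near-doubling applies only near independence. If only one of the two nulls is true, there is no inflation beyond that test's own 5%.

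The joint rate matters only if the secondary is used for a stand-alone confirmatory claim, which the documents neither state nor exclude.

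**What to change.** Replace the rule in all five places: SAP 6.1.2, 9.1.1 and 9.1.5, and protocol 5.9 under the Aim 1 sample size and under the analysis of the secondary outcome. Changing the SAP alone would make the two documents disagree. Suggested content: the primary outcome is tested at 0.05 (two-sided); the secondary is tested at 0.05 (two-sided) only if the primary is significant; otherwise the secondary difference and its 95% confidence interval are reported as supportive, with no claim of significance. Drop the sentence that reasons from the number of secondary outcomes.

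The cost is wording, plus the loss of a secondary claim after a null primary. The primary's alpha, power and sample size do not change. At 90% power on each outcome, the chance of a secondary claim falls from 90% to about 81-87%.

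Timing matters. SAP section 9 allows changes up to final data lock and before unblinding, and SAP 8.1 puts the database freeze at 10/19/2023. The documents do not show whether unblinding has taken place. If the window has closed, leave the rule as written and label the secondary result supportive when reporting it.
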